4.1 Inclusion Criteria

Patients must meet all of the following inclusion criteria to be eligible for enrollment into the study:

1. Histologically confirmed NSCLC with metastatic or unresectable, locally advanced disease.
2. Receipt of at least one prior platinum-containing chemotherapy or licensed immunotherapy regimen in the advanced disease setting.
3. Molecular analysis of patient-derived samples using a Sponsor- approved method and laboratory that demonstrates a genetic alteration activating *MET* in tumor tissue and/or ctDNA. If eligibility is established using a Sponsor-approved local laboratory, a tumor tissue specimen and/or blood sample is expected to be available for retrospective sequencing in the central laboratory selected by the Sponsor.
4. Measurable disease, as per RECIST version 1.1.
5. Eastern Cooperative Oncology Group (ECOG) performance status 0, 1, or 2 (Appendix 1).
6. Adequate bone marrow and organ function demonstrated by:
 - a. Absolute neutrophil count $\geq 1,000/\text{mm}^3$ ($\geq 1.0 \times 10^9/\text{L}$)
 - b. Alanine aminotransferase (ALT) and aspartate aminotransferase (AST) $\leq 2.5 \times$ Upper Limit of Normal (ULN), or $\leq 5.0 \times$ ULN for patients with documented liver metastases. Alkaline phosphatase levels $\leq 2.5 \times$ ULN. In the presence of extensive bone metastases, there is no upper limit for alkaline phosphatase.
 - c. Total bilirubin $\leq 1.5 \times$ ULN or $\leq 3.0 \times$ ULN for patients with Gilbert Syndrome or documented liver metastases.
7. ≥ 18 years of age.
8. Women of child-bearing potential (WOCBP) or men whose partner is a WOCBP agrees to use contraception while participating in this study, and for a period of 6 months following termination of study treatment.

9. Completed informed consent process, including signing IRB/EC-approved informed consent form.
10. Willing to comply with clinical trial instructions and requirements.

4.2 Exclusion Criteria

Patients presenting with any of the following will not be included in the study:

1. Prior treatment with a small molecule or antibody inhibitor of MET or HGF.
2. Prior positive test for *EGFR* mutation or *ALK* gene rearrangement
 - Testing and documentation is required for patients with adenocarcinoma histology;
 - Testing is not required for patients with non-adenocarcinoma histology; however if documentation of a positive test is available, the patient will not be eligible.
3. Most recent prior systemic therapy (e.g. chemotherapy or immunotherapy) or investigational agent discontinued ≤ 2 weeks before first dose date.
4. Absence of recovery from the adverse effects of prior therapy at the time of enrollment to \leq Grade 2 (excluding alopecia).
5. History of stroke or transient ischemic attack within the previous 6 months.
6. Any of the following cardiac abnormalities:
 - a. Unstable angina pectoris,
 - b. Congestive heart failure \geq NYHA Class 3, or
 - c. QTc > 480 msec.
7. Known or suspected presence of another malignancy that could be mistaken for metastatic NSCLC during disease assessments.
8. Symptomatic or uncontrolled brain metastases requiring current treatment (less than 4 weeks from last cranial radiation, 2 weeks from stereotactic radiosurgery [gamma knife], or 2 weeks from last steroids). Known conditions associated with significant risk of intracranial bleeding including but not limited to vascular malformations and pituitary adenoma.
9. Inability to swallow oral medications or pre-existing gastrointestinal disorders that might interfere with proper absorption of oral drugs.

10. Known hypersensitivity to any of the components of the MGCD265 Drug Product.
11. Pregnancy. WOCBP must have a negative serum or urine pregnancy test documented within the screening period prior start of study drug.
12. Breast-feeding or planning to breast feed during the study or within 6 months after study treatment.
13. Any serious illness, uncontrolled inter-current illness, active or uncontrolled infection, or other medical history, including laboratory results, which, in the Investigator's opinion, would be likely to interfere with the patient's participation in the study, or with the interpretation of the results.

4.3 Life Style Guidelines

Patients who are biologically capable of having children and sexually active must agree to use an acceptable method of contraception for the duration of the treatment period and for at least 6 months after the last dose of study treatment. The investigator will counsel the patient on selection of contraception method and instruct the patient in its consistent and correct use. Examples of acceptable forms of contraception may include:

1. Oral, inserted, injected or implanted hormonal methods of contraception, provided it has been used for an adequate period of time to ensure effectiveness.
2. Correctly placed copper containing intrauterine device (IUD).
3. Male condom or female condom used WITH a spermicide
(Exception: in the European Union, this option does not meet criteria for highly effective contraception and therefore is not an acceptable form of contraception for this study; please refer to the following guidance:

http://www.hma.eu/fileadmin/dateien/Human_Medicines/01About_HMA/Working_Groups/CTFG/2014_09_HMA_CTFG_Contraception.pdf)
4. Male sterilization with confirmed absence of sperm in the post-vasectomy ejaculate.
5. Bilateral tubal ligation or bilateral salpingectomy.

The investigator will instruct the patient to call immediately if the selected birth control method is discontinued or if pregnancy is known or suspected.

Note: Women are considered post-menopausal and/or not of child bearing potential if they have had 12 months of natural (spontaneous) amenorrhea with an appropriate clinical profile (e.g., age appropriate, history of vasomotor symptoms) or have had surgical bilateral oophorectomy (with or without hysterectomy) or tubal ligation at least

6 months ago. In case of any ambiguity, the reproductive status of the woman should be confirmed by hormone level assessment.

4.4 Enrollment into Study

Genotyping of the tumor sufficient for establishing study eligibility may have been performed historically or more recently for the purpose of considering enrollment in this study. In all cases, informed consent for tumor genotyping (using tumor tissue or ctDNA) must be documented prior to submission of samples for testing. The informed consent for tumor testing may be performed in accordance with established institutional practice, or using the study-specific, IRB-approved pre-screening informed consent associated with this study.

If the Sponsor-provided central laboratory is used to perform tumor genotyping to establish eligibility for the study, a 14-day turn-around time should be expected from the time of receipt of adequate samples at the central lab to test results returned to the study site. Questions concerning adequacy of samples will cause delay beyond this timeframe.

Following completion of the full, study-specific informed consent process and review of all screening procedures, patient eligibility will be confirmed by appropriately qualified staff at the investigational site. Patients will be enrolled by entry into a patient registration log provided by the Sponsor and maintained by the study site and completion of the patient registration procedure detailed in the Study Manual. Each patient will be assigned a sequential number by the study site. The patient number must be used on all documentation and correspondence with the Sponsor, Contract Research Organization (CRO) and laboratory vendors.

5 STUDY TREATMENT

5.1 Study Drug Management

5.1.1 Formulation and Packaging

MGCD265 study drug will be supplied by the Sponsor. At the beginning of the study, the presentation was soft gel capsules containing the free-base form of MGCD265 and inert excipients: Miglyol[®], Labrafil[®], fractionated coconut oil, Capsule Gel 60, Gelatin 195 Acid Bone and glycerin. Dosage strength is 150 mg (white opaque capsule), calculated as free-base corrected for purity.

Soft gel capsules are supplied in 40 count, high-density polyethylene (HDPE) bottles with child resistant closures. Bottles will be labeled in compliance with the legal requirements per country. Labels will be printed in the languages required in the countries in which the study is conducted.

MGCD265 Spray-Dried Dispersion [SDD] tablet formulation is being introduced with a protocol amendment (Version 2.0). Dosage strength will be 100 mg and 250 mg. Inert excipients in the SDD tablet include hydroxypropylmethyl cellulose (HPMC), Avicel[®] (or equivalent), Kollidon[®] (or equivalent), sodium bicarbonate, sodium chloride, Syloid[®] (or equivalent), and magnesium stearate, as necessary.

SDD tablets will be supplied in HDPE, white opaque bottles. A tamper-proof heat induction seal and a child-resistant closure are used. Tablet bottles will be received by the pharmacy in foil pouches that are to be kept intact until the bottles are dispensed to the patient. Bottles will be labeled in compliance with the legal requirements per country. Labels will be printed in the languages required in the countries in which the study is conducted.

Refer to the Pharmacy Study Manual for details on available study drug presentations, unit dose strengths, bottle sizes, and number of units per bottle supplied.

5.1.2 Drug Storage and Accountability

MGCD265 study drug should be stored as directed on the package labeling. The storage area should be secure with limited access and monitored for temperature using a calibrated thermostat. Shelf-life evaluation of the intact bottles is ongoing. Available stability data for the soft-gel capsules support ≥ 24 -months shelf-life when stored at room temperature (suggested temperature range 15-30°C, 59-86°F).

SDD tablets, while stored in the study site pharmacy, should be kept in the unopened foil pouches under refrigerated conditions (suggested temperature range 2-8°C, 36-46°F). Once dispensed to patients, bottles should be stored at room temperature (suggested temperature range 15-30°C, 59-86°F). Available stability data for the SDD tablets support > 12 months shelf-life for pharmacy storage at refrigerated conditions and > 4 months shelf-life when stored at room temperature after dispensation to the patient.

All study treatment supplies will be accounted for in the drug accountability inventory forms supplied by the Sponsor or using forms according to local site procedures that include all required information. The drug accountability inventory forms must identify the study drug, including batch or lot numbers and account for its disposition on a patient-by-patient basis, including specific dates and quantities. The forms must be signed by the individual who dispensed the drug.

5.1.3 Preparation and Dispensing

Only qualified personnel who are familiar with procedures that minimize undue exposure to them and to the environment should undertake the preparation, handling, and safe disposal of chemotherapeutic agents.

Study site personnel should dispense to patients the appropriate number of study drug units of each strength to support a 21-day cycle. An additional number equivalent to

two dosing days may be dispensed at the discretion of the study site to provide for holidays or inclement weather. Study drug should be dispensed in the Sponsor provided HDPE bottles with child resistant closures. Patients should be made aware of the storage temperature requirements.

5.1.4 Compliance

Study site personnel should provide each patient with dosing information and review it with the patient during clinic visits. Patients will be asked to record their daily dosing on Sponsor provided diary cards and report any missed doses or lost study drug at the next clinic visit. Patients will also be told to bring study drug bottle(s) (empty or not) with them to the clinic visit for a compliance check and unit count. Study site personnel will record compliance information in the source document and on the CRF and retain the bottle(s) until a monitor has completed reconciliation. See the Study Manual for additional details regarding compliance and reconciliation.

5.1.5 Destruction

At the end of the study, all unused drug supplies must be destroyed in accordance with local Standard Operating Procedure provided to the Sponsor for the Trial Master File, or returned to the Sponsor or its appointed agent, as directed by the Sponsor.

5.2 Administration

MGCD265 study drug will be administered orally twice daily (BID) in 21-day cycles. The starting dose of MGCD265 using the soft gelatin capsules was 1050 mg BID. The starting dose using the SDD tablets will be 750 mg BID. At the time of protocol amendment (Version 2.0) approval at each institution, newly enrolled patients will begin dosing at 750 mg BID with the SDD tablet formulation. Ongoing patients who initiated treatment with soft-gel capsules will be allowed to switch to the SDD tablet formulation at their next treatment cycle. The dose level of the SDD tablet will need to be discussed on a case-by-case basis with the Sponsor prior to the patient receiving the SDD tablet formulation.

MGCD265 doses should be taken approximately every 12 hours at approximately the same times each day, on an empty stomach (1 hour fast before each dose and no food for a minimum of 1 hour after each dose). Each dose should be taken with approximately 200 mL of water.

A food effect evaluation is currently being conducted in the MGCD265 Phase 1 study. If the outcome of that evaluation indicates that patients may take MGCD265 SDD tablets with food, this change will be communicated to participating institutions.

If the patient vomits after taking the study drug, s/he should not make up the missed dose or increase the next dose.

5.2.1 Dose Modification

Study treatment-related adverse events that are intolerable or severe will be managed by treatment interruption and/or dose reduction depending on the circumstance. In response to observed toxicity, daily doses should be reduced by steps of at least 15-20% within the constraints of the available capsule or tablet dose strengths. Necessary dose reductions will typically be made in sequential steps but, under some circumstances, dose reduction by two steps (i.e., 30-40%) may be advisable and may be considered in consultation between the investigator and Sponsor (See Table 5 and Table 6). Dose reductions below the current guidelines may be allowed after consultation between the investigator and Sponsor. Patients requiring greater than 3 weeks to recover from drug-related toxicity should be considered for discontinuation from study treatment.

Table 5: Dose Adjustment Guidelines Soft Gel Formulation

Soft Gel - Capsule Formulation		
Dose Level	265 Daily Dose (BID Dose)	Number of capsules (150 mg capsule strength)
0 (Starting Dose)	2100 mg (1050 mg BID)	14 total (7 BID)
-1	1800 mg (900 mg BID)	12 total (6 BID)
-2	1500 mg (750 mg BID)	10 total (5 BID)

Table 6: Dose Adjustment Guidelines Spray Dried Dispersion Formulation

Spray Dried Dispersion – Tablet Formulation		
Dose Level	265 Daily Dose (BID Dose)	Number of tablets (100 mg and 250 mg tablet strength)
0 (Starting Dose)	1500 mg (750 mg BID)	6 total (3 BID) [3-250 mg BID]
-1	1200 mg (600 mg BID)	6 total (3 BID) [2-250 mg BID; 1-100 mg BID]
-2	1000 mg (500 mg BID)	4 total (2 BID) [2-250 mg BID]

Dosage interruptions to assess or treat intercurrent illnesses are allowed as needed in the judgment of the investigator.

5.2.2 Adverse Event Management Guidelines

Management of toxicities \geq Grade 3 and considered to be treatment-related should include treatment interruption until resolution of toxicity to \leq Grade 1 or to baseline

value. If the toxicity may be adequately managed by routine supportive care (such as anti-emetics, anti-diarrheals, or electrolyte supplementation), treatment may be resumed at the same dose; if not, treatment may be resumed at a reduced dose as described in Table 7. Recurrence of the toxicity may be managed similarly. If treatment is interrupted for more than 3 weeks, permanent discontinuation from study treatment should be considered.

Table 7: Dose Modifications – Treatment-Related Toxicities

Toxicity	Treatment Delay	Dose Modification
< Grade 3	May be implemented based on Investigator and patient discretion	
Grade 3 or 4, manageable with routine supportive care	Hold until \leq Grade 1 or return to baseline	Not required
Grade 3 or 4, not manageable with routine supportive care	Hold until \leq Grade 1 or return to baseline	Resume at a dose level one or more levels below that inducing the toxicity

5.2.2.1 Management of Diarrhea

Prevention and treatment of diarrhea should be aggressive to limit patient morbidity and to prevent potentially premature study drug discontinuation. Example treatment regimens are recommended here and in Section 5.4.1, Concomitant Medications.

Prophylactic anti-diarrheal treatment may be implemented at the discretion of the investigator. A regimen recommended for primary prophylaxis for diarrhea is loperamide 2-4 mg beginning with the first dose of MGCD265, followed by 2 mg every 6–8 hours. Loperamide use may be titrated as needed.

To date, diarrhea has been effectively managed after onset in most subjects by symptomatic treatment with Imodium[®] (loperamide) and, when indicated, with the addition of Lomotil[®] (diphenoxylate and atropine). Patients treated with MGCD265 should be given instructions to be aware of the potential of developing diarrhea while taking MGCD265 and to start treatment with loperamide immediately upon the first sign of diarrhea. If there is no improvement in severity of symptoms within 24 hours, additional anti-diarrheal medication in the form of Lomotil[®] should be added. If this does not effectively control symptoms, patients should be instructed to contact their physician and their dose held until resolution of symptoms followed by a dose reduction as indicated per protocol. Patients with severe or prolonged diarrhea should be observed and treated for dehydration.

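### The diarrhea guidance gives patients no severity-based prompt to stop dosing and call, so Table 7's hold for Grade 3-4 toxicity may start late or be missed

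*Combined protocol and SAP*

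**What the plan says.** Three layers of protocol text apply.

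- **General rule (section 5.2.1).** "Study treatment-related adverse events that are intolerable or severe will be managed by treatment interruption and/or dose reduction", depending on the circumstance.
- **Grade 3 rule (section 5.2.2 and Table 7).** Management of toxicities that are Grade 3 or higher and "considered to be treatment-related should include treatment interruption until resolution of toxicity" to Grade 1 or lower, or to baseline. The Table 7 row headed "Grade 3 or 4, manageable with routine supportive care" still calls for a hold; what it waives is the dose reduction.
- **Diarrhea (section 5.2.2.1).** Patients are to be told "to start treatment with loperamide immediately upon the first sign of diarrhea". The next step is conditional: "If there is no improvement in severity of symptoms within 24 hours, additional anti-diarrheal medication", namely Lomotil, is to be added. Only then comes the call and the hold: "If this does not effectively control symptoms, patients should be instructed to contact their physician and their dose held until resolution of symptoms". The section closes with "Patients with severe or prolonged diarrhea should be observed and treated for dehydration". It describes its regimens as examples.

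On exposure, section 5.2 states: "MGCD265 doses should be taken approximately every 12 hours at approximately the same times each day". Section 5.1.3 has each patient supplied with enough drug for a 21-day cycle.

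**The concern.** The Grade 3 hold can operate only once the site knows about the event. Transaminase rises, covered in the next subsection with grade-specific actions, are found by the site through laboratory tests. Diarrhea is noticed first by the patient, at home, with drug in hand. The sequence in 5.2.2.1 gives that patient a reason to call only when two drugs have failed, whatever the severity.

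This matters most for the case that Table 7 singles out: Grade 3 diarrhea that responds to supportive care. Table 7 requires a hold. A patient following 5.2.2.1 literally, whose diarrhea improves on loperamide, never reaches the stated trigger.

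At stake is continued dosing through severe diarrhea, with a dehydration risk that the section itself recognizes. Section 1.2.3 reports diarrhea as the most frequent related event in single-agent use (62%) and the most frequent related Grade 3 event (8%).

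**Working it through.** The protocol states no figure for this delay, so there is none to reproduce. The check is a dose count, followed by a bound on how many patients could be concerned.

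**Inputs**
- Dosing interval: about 12 hours (section 5.2). Daily dose divided by BID dose equals 2 at every level of Tables 5 and 6.
- Loperamide step: 24 hours (section 5.2.2.1).
- Lomotil step: no length stated, and the text does not say who adds the drug.
- Related Grade 3 diarrhea: 8% (section 1.2.3).
- Enrollment: 4 arms of 45 patients, up to 290 with expansion (section 9.1).

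**1. Does the site find out anyway?** With 21-day cycles, the Table 2 visits fall on about days 1, 15, 22, 36, 43 and 64. The gaps are 14, 7, 14, 7 and then 21 days, before the ±2-day windows. Between visits the site may depend on the patient's call.

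**2. Doses in the loperamide step.** 24 h / 12 h = 2 doses, whatever the time of onset within the dosing interval.

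| Formulation | Starting dose | Level -1 | Level -2 |
|---|---|---|---|
| SDD tablet | 2 × 750 = 1500 mg | 2 × 600 = 1200 mg | 2 × 500 = 1000 mg |
| Soft gel | 2 × 1050 = 2100 mg | 2 × 900 = 1800 mg | 2 × 750 = 1500 mg |

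**3. Doses if Lomotil is then tried before a call.** The trial length is an assumption. Total doses = (24 + Lomotil hours) / 12.

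| Assumed Lomotil trial | Doses from onset |
|---|---|
| 0 h | 2 |
| 6 h | 2 to 3 |
| 12 h | 3 |
| 24 h | 4 |
| 48 h | 6 |

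Two is therefore the minimum when the whole sequence is followed, and the text sets no maximum. The count starts at the first sign of diarrhea, so these are doses taken at Grade 3 only if the diarrhea is Grade 3 from onset.

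**4. Patients to whom the gap could apply.** At 8%: 0.08 × 290 = 23.2 at maximum enrollment, and 0.08 × 180 = 14.4 without expansion (4 × 45 = 180). If SDD tablets halved the rate, 0.04 × 290 = 11.6. The halving is an assumption; section 1.2.3 reports only a trend toward fewer and milder events. These are patients with related Grade 3 diarrhea, not patients with a delayed hold. The documents give no rate for the latter.

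**The case against.** The strongest reply is that the safety rule already exists. Sections 5.2.1 and 5.2.2 and Table 7 cover severe related diarrhea. Section 5.2.2.1 is guidance to investigators built on example regimens, and the sheet that patients actually receive is not in the documents. Table 7's first row leaves delays below Grade 3 to investigator and patient discretion. Section 10.2 makes the investigator responsible for informing patients and monitoring their safety. Table 2's introduction provides for unplanned assessments, and observing a patient with severe diarrhea presupposes contact. Nothing forbids an early call, and if the site is the one adding Lomotil, contact comes at about 24 hours.

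Much of this stands. A reader might infer that 5.2.2.1 contradicts or overrides Table 7. It does not: it is a subsection of 5.2.2 and nowhere exempts diarrhea from the Grade 3 hold. Nor can a gap in the patients' own instructions be shown from these documents.

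An earlier hold would also lower early exposure only in part. Assuming first-order decline at the single-dose mean half-lives in Table 4, the fraction remaining 24 hours after stopping is 0.5^(24/30.9) = 0.58 for SDD tablets and 0.5^(24/36.7) = 0.64 for soft gel capsules.

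What does not stand is the conclusion that nothing needs changing. The discretion row concerns events below Grade 3. The duty to inform is general, and the sentence on observation speaks to those already treating the patient. None of them tells a patient at home with severe diarrhea to stop and call, and the one sequence that does address the patient puts that step last.

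**Conclusion.** The point holds as a patient-safety wording gap. The only stated trigger in 5.2.2.1 for contact and a hold is failure of loperamide and then Lomotil, with no grade and no limit on the second step. Followed literally, it can delay the hold that Table 7 requires, or bypass it when loperamide works.

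The size is at least 2 further doses: 1500 mg at the SDD starting dose, 2100 mg at the soft gel starting dose. This rests on three assumptions: the diarrhea is Grade 3 from onset, the patient follows the sequence without calling sooner, and no earlier trigger appears in the patient instructions.

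Two stronger readings are tempting. A reader might take 2 as the expected number of doses at Grade 3, but gradual worsening, an earlier call or a longer Lomotil trial would each change it. A reader might also take 12 to 23 patients as a forecast of delayed holds. Those figures count related Grade 3 diarrhea at maximum enrollment, under an assumed and an observed rate, and say nothing about how often a hold would be late.

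No efficacy endpoint, error rate or sample size is affected. The change is worth making because it is cheap and concerns the drug's most common related toxicity.

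**What to change.** Add to section 5.2.2.1, and to the patient instructions if they do not already say so:

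*For severe diarrhea (CTCAE Grade 3 or higher, described in plain words), stop MGCD265 and contact the site immediately. If it is treatment-related, hold until Grade 1 or lower, or baseline, and resume per Table 7. The stepwise loperamide/Lomotil sequence without a hold applies only below Grade 3, and patients should contact the site if symptoms are not controlled within a stated time (for example 24 hours) after Lomotil is added.*

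The cost is a few sentences, made by amendment or Administrative Letter with IRB/EC approval before use (section 13.1). In operation, expect some extra calls and some short holds for diarrhea that the investigator later judges unrelated.
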